#### Specific Aims:

**Aim 1:** To determine the effectiveness of Self-Administered Nitrous Oxide (SANO) in decreasing patient perceived anxiety and pain related to prostate needle biopsy.

*Hypothesis 1.1: Patients receiving periprocedural SANO will have decreased anxiety during the procedure, as measured by STAI (State-Trait Anxiety Inventory) score, situational pain catastrophizing scale (SPCS) and patient vital signs.*

*Hypothesis 1.2: Patients receiving periprocedural SANO may have a decrease in pain as measured by VAS (visual analogue scale) score and patient vital signs.*

**Aim 2:** To demonstrate that the SANO at the time of prostate biopsy does not significantly increase burden on Urologist productivity, nor increase the difficulty of performing the biopsy.

*Hypothesis 1.1: Administration of periprocedural SANO will not significantly lengthen the time of the procedure relative to local anesthetic alone.*

*Hypothesis 1.2: Administration of periprocedural SANO will result in minimal side effects for the patients and will allow the patient to drive home independently.*

*Hypothesis 1.3: Administration of periprocedural SANO will allow the operating Urologist to perform the procedure with the same ease as on those patients who do not have SANO.*

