###### **Baseline Assessment:**

After informed consent has been obtained, the patient will be directed to a REDCap questionnaire that will collect demographics, general medical history, and prior prostate biopsy information (See Pre-Procedure Evaluation Survey). This will be reviewed by research personnel to confirm eligibility to participate in the study based on pre-determined inclusion and exclusion criteria. If they do not qualify for the study, they will not be randomized to either arm, and will undergo a standard template biopsy with local anesthesia only.

In addition, patients will complete the Brief Pain Inventory, a well-validated measure that assesses intensity of current pain and interference of pain in the patient's life (Dworkin, 2005). If the patient

does not complete these two questionnaires electronically before the day of procedure, they will be offered the opportunity to complete on the day of their procedure prior to the biopsy.

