### **Periprocedural Data Collection**

After the biopsy, the patient will be moved to the recovery room for routine post-procedure vitals as well as completion of post-procedure STAI score and Situational Pain Catastrophizing Score (S-PCS) on a tablet computer. The S-PCS was derived from the Pain Catastrophizing Scale (PCS), a validated questionnaire used to measure catastrophic thinking associated with pain. We will also question for side effects of the nitrous oxide including nausea, vomiting, dizziness, drowsiness, with an option to enter “other” as a manual entry. An additional question of whether the patient feels comfortable driving home independently will be assessed.

Patients who do not have an escort planned after their biopsy will be asked to perform two hand-eye coordination tests after completion of post-procedure surveys. First, the participants will be verbally instructed to extend one arm in front of them, and place one finger to the tip of their nose. After, the Trail-making test Part B will be administered. This test has been promulgated by the American Medical Association to screen for driving fitness. The Trails-making Part B test will ask participants to connect numbers (1-13) to letters (A-L) randomly written on a page. This test is scored according to accuracy and time required to make the connections (Joseph, 2013). If the participant is unable to accurately complete these tests, additional recovery time will be required. The participant’s performance and disposition will be included in the documentation of study procedures performed during the visit.

The urologist who performed the biopsy procedure will be provided the Operator Survey to assess the ease of procedure.

Chart review will be performed to capture any unanticipated ED visits, admissions, or office visits for the 7 days following the procedure. We will also record any phone calls that are made by patients within 7 days of procedure that pertain to procedure concerns.

Lastly, participants who completed study procedures during their prostate biopsy will be asked to complete a survey 2-10 months following the study biopsy. This brief survey is designed to understand participant’s recollection of pain and anxiety during the biopsy. The survey is estimated to take 2-3 minutes to complete.

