### Data Analysis

All data will be collected and stored securely using the REDCap system. Data will be managed and analyzed by the PI and biostatistical support team at the BIDMC FIRST program. A Data Transfer Agreement will be created to allow for the study team's statistician, [name] MD/PhD at Brigham and Women's Hospital, to obtain and perform statistical analysis on de-identified data. At the conclusion of the study, de-identified study data will be exported out of REDCap and sent to [name] in a secure file via email message. Data will not be transferred until this agreement is approved and fully executed by both parties.

Primary outcome measure is patient anxiety and pain levels in the N2O group vs the oxygen only group as measured by the VAS and VAS A scores. We are specifically interested in the difference in scores between the two groups. Prostate biopsy mean VAS score with local anesthetic is around 3-4. We will also obtain a baseline pain index between the two groups. We will compare the perioperative VAS and VAS-A scores to the retrospective VAS and VAS-A scores collected during the survey administered 2-10 months after their biopsy.

We will also be obtaining 6 question Situational Pain Catastrophizing Scores for both groups and will compare the variation in response. Patients who have had a prior biopsy will also fill out a 13 question Pain catastrophizing score, which we will use as a baseline measure for biopsy related anxiety and hesitation.

Additional metric will include duration of biopsy, as measured by time in/time out of the procedure room for patients administered either nitrous or control oxygen when compared to patients who do not consent to the study (and will have no gas applied). Operator ease in performing the biopsy will be measured by 3 simple questions assessing patient positioning and ease of transrectal probe insertion. Prostate biopsies are generally performed as an outpatient procedure and patients can drive themselves home in most situations. Post biopsy side effects and ability of the patient to drive themselves home will be used as a surrogate to determine practicality of administering SANO in the outpatient setting.

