## **B7. STUDY LOCATION**

### **Privacy**

The study will be conducted on the premises of BIDMC Longwood Campus. We will obtain lists of patients intended for prostate biopsies in the following week, and study team members will review the OMR records for inclusion and exclusion criteria. The patient will be contacted by phone either from in-office phone call or through Doximity phone application (which provides the BIDMC Urology office as the caller ID). We will ask the patient whether they are in a location that affords privacy for discussion of medical information. If they are not, we will arrange an appropriate time when the patient will have privacy for study discussion. Phone interviews by study team members will be conducted in private space to avoid the interview being overheard.

Pre-procedure questionnaires will be emailed to private patient email via the REDCap server. Data collected will be kept within the REDCap server. Access to our REDCap will only be allowed for study team members who are trained in protecting PHI.

Operator Surveys will be on paper forms with patient identifying sticker on the form. At the end of the biopsy, the data will be input into the REDCap system by a study team member, and the paper version will be disposed of in a disposal unit intended for medical information waste.

Pre-procedure and post-procedure VAS, VAS-A score and Situational Pain Catastrophizing Score (S-PCS) and Trails-making Part B tests will be obtained in a private exam room where only the patient, study team members, and clinical staff measuring vitals will be present. Questionnaire answers will be input by the patient into a tablet computer. The tablet computer will be wiped with sanitizing wipe between uses given current COVID pandemic.

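### The pain-catastrophizing baseline is planned only for men with a prior biopsy and has no stated time point, so first-biopsy men have no clearly planned baseline for the S-PCS

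*Combined protocol and SAP*

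**What the plan says.** Hypothesis 1.1 (Specific Aims) lists, among the measures of reduced anxiety, "situational pain catastrophizing scale (SPCS) and patient vital signs". Periprocedural Data Collection places the S-PCS in the recovery room, together with the post-procedure STAI, and explains its origin: "The S-PCS was derived from the Pain Catastrophizing Scale (PCS), a validated questionnaire used to measure catastrophic thinking associated with pain".

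For analysis, the Data Analysis section plans to obtain "6 question Situational Pain Catastrophizing Scores for both groups and will compare the variation in response". The next sentence introduces the parent scale: "Patients who have had a prior biopsy will also fill out a 13 question Pain catastrophizing score, which we will use as a baseline measure". That sentence goes on to say what the baseline is for: anxiety and hesitation related to biopsy.

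The visit descriptions do not mention the 13-item form. Baseline Assessment has a REDCap questionnaire to "collect demographics, general medical history, and prior prostate biopsy information (See Pre-Procedure Evaluation Survey"), and adds that "patients will complete the Brief Pain Inventory". It then provides for the patient who "does not complete these two questionnaires electronically before the day of procedure", so it counts two forms. Pre-procedure Evaluation lists the STAI and VAS only.

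The Privacy section (B7) differs. It refers to "Pre-procedure and post-procedure VAS, VAS-A score and Situational Pain Catastrophizing Score (S-PCS") and the Trail-making test as obtained in a private room, with no limit by biopsy history.

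The eligibility criteria do not restrict biopsy history, so men having a first biopsy can enrol. Their expected share is not given.

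**The concern.** The plan has a catastrophizing outcome for everyone and a catastrophizing baseline for some. The S-PCS comes from the PCS, and the PCS sentence directly follows the S-PCS sentence, so the PCS is the natural covariate for it. As written, that covariate would exist in only one biopsy-history group.

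The protocol's own background makes this trait worth measuring in all patients. It names pre-biopsy anxiety as a factor in biopsy pain and says the psychological impact is greater in men who need a repeat biopsy. The Possible Benefits section hopes to identify patient factors that predict who gains from nitrous oxide. Catastrophizing cannot be examined that way in first-biopsy men unless it is measured in them before treatment.

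The missing time point matters separately. A score is usable as a baseline only if it is taken before the gas is given, and the readable text does not fix this for the PCS.

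**Working it through.** **Where each instrument sits**

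| Section | Timing | Instruments named |
|---|---|---|
| Baseline Assessment | before randomisation | history and prior-biopsy questionnaire; Brief Pain Inventory |
| Pre-procedure Evaluation | day of biopsy, before gas | STAI, VAS |
| Periprocedural Data Collection | after biopsy | STAI, S-PCS |
| Privacy (B7) | can be read as before and after | VAS, VAS-A, S-PCS, Trail-making B |
| Data Analysis | none stated | 13-item PCS, prior-biopsy men only |

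The PCS has no row with a time. The S-PCS has two incompatible ones. The Privacy list is loose, because it also contains the Trail-making test, which the procedure text gives only after the biopsy. It therefore does not establish that a pre-procedure S-PCS is planned.

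**The plan's own figure.** The only calculation in the documents is the sample size, which concerns the STAI and not the S-PCS. With a 4-point difference, SD 8, two-sided alpha 0.05 and 80% power:

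- Normal approximation: n = 2(1.96 + 0.842)² × (8/4)² = 62.8, so 63 per group.
- t-test: 63.77, so 64 per group, as stated.
- Allowance for loss: 64/(1 − 0.15) = 75.3, so 76 per group, as stated.

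The figure reproduces, and nothing here changes it.

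**Precision from a complete baseline.** Adjusting for a covariate with correlation r to the outcome multiplies the standard error by sqrt(1 − r²). The documents do not give r, so a range is assumed.

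| Assumed r | sqrt(1 − r²) | Reduction in standard error |
|---|---|---|
| 0.3 | 0.954 | 5% |
| 0.5 | 0.866 | 13% |
| 0.7 | 0.714 | 29% |

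**Complete against partial baseline.** Suppose a fraction f of men have the PCS, and the adjusted estimate in those men is pooled with the unadjusted estimate in the rest. The effective number per arm is 64f/(1 − r²) + 64(1 − f). For an illustrative 0.5 SD effect on the S-PCS, power is Φ(0.5/sqrt(2/n_eff) − 1.96).

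| r | No covariate | PCS in 25% | PCS in 75% | PCS in all |
|---|---|---|---|---|
| 0.3 | 80.7% | 81.7% | 83.4% | 84.3% |
| 0.5 | 80.7% | 83.7% | 88.5% | 90.4% |
| 0.7 | 80.7% | 88.3% | 96.0% | 97.7% |

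At r = 0.5 the effective numbers per arm are 69.3, 80.0 and 85.3 with the PCS in 25%, 75% and all men. Relative to a partial baseline that is actually used, full collection lowers the standard error by 1 − sqrt(69.3/85.3) = 10% or 1 − sqrt(80.0/85.3) = 3%. The 13% applies relative to no adjustment.

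**The case against.** The strongest objection is that the plan never calls the PCS a baseline for the S-PCS. Its stated purpose is anxiety and hesitation about biopsy, and restricting it to men who have had one is understandable on that purpose. The plan states only a between-group S-PCS comparison, with no adjustment. This stands: treating the PCS as the S-PCS covariate is a sensible inference, not something the plan promises.

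A reader might infer that the S-PCS comparison is invalid, or that first-biopsy men would drop out of it. The documents support neither. Allocation is randomised 1:1, so the post-procedure comparison in all patients is unbiased without a baseline. No section limits it to men with a prior biopsy, and a covariate known in only some men need not exclude the others.

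A reader might also infer that first-biopsy men certainly have no baseline. That goes too far, because the Privacy section can be read as a pre-procedure S-PCS for everyone. Nor can it be said that the PCS is scheduled nowhere: Figure 1 and the Pre-Procedure Evaluation Survey are not shown in the text available, and either might place it. The suggestion that the PCS would be given after the gas is speculation about a form the plan labels a baseline.

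Finally, identifying predictors of benefit is a hope expressed under Possible Benefits, not an aim. Other pre-treatment measures (STAI, VAS, Brief Pain Inventory) are planned for every patient.

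**Conclusion.** The point holds as a gap in the assessment schedule and a missed, cheap gain in precision; it is not a threat to validity. The PCS is limited to one biopsy-history group and has no readable time point, and the sections disagree on whether the S-PCS is also taken before the procedure.

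The size is a standard error about 5% to 29% smaller for an all-patient S-PCS comparison, relative to no adjustment, for assumed r from 0.3 to 0.7. The gain is smaller than that if the partial baseline would have been used anyway. Both the correlation and the share of men with a prior biopsy are assumptions. The power figures further assume a 0.5 SD effect on the S-PCS, 64 evaluable men per arm, and the same correlation and variance in both biopsy-history groups.

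**What to change.** 1. Add the 13-item PCS, worded for pain in general, to the REDCap baseline set for every participant, completed before randomisation. Randomisation already follows the baseline assessment, so the sequence does not change. Keep any biopsy-specific wording as an extra for men with a prior biopsy, which preserves the purpose now stated.
2. State in Data Analysis that the all-patient S-PCS comparison will be adjusted for the baseline PCS.
3. Reconcile Pre-procedure Evaluation, Periprocedural Data Collection and Privacy on whether a pre-procedure S-PCS is taken. If it is taken in everyone, say in advance which of the two scores is the covariate and which is descriptive.

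The cost is a protocol amendment and one form, already in use for some participants, added to a REDCap link already being sent. The downside is a few more minutes of questionnaires for first-biopsy patients.

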## B2. SIGNIFICANCE AND BACKGROUND FOR THE STUDY

### Burden of Transrectal Prostate Biopsies in the US

The number of prostate biopsies performed on US men annually is nearing 2 million (Wolinsky, 2021). Transrectal prostate needle biopsy is a very common procedure in the US that is associated with significant anxiety and discomfort for men. Historically, a prostate needle biopsy is performed via a transrectal ultrasound probe with a lidocaine local anesthetic block, without sedation or general anesthesia. In part, the prostate biopsy is performed without sedation or anesthesia due to added cost and time associated with an anesthesia team required for most anesthesia agents.

Until the early 2000s, prostate biopsy was frequently performed without the aid of local anesthetic. Current practice is to perform prostate biopsies with a periprostatic block using 10 ml of 1% lidocaine. Even with an anesthetic on board, studies have demonstrated the significant psychological impact of prostate needle biopsies, and this is further compounded in those patients requiring repeat biopsy.

Factors influencing the development of pain during a prostate biopsy can be divided into patient-associated factors (younger age, smaller prostate, and pre-biopsy anxiety) and procedure-associated factors (number of cores, use of local lidocaine block). With the advent of MRI fusion technology, we can now target suspicious areas with greater accuracy. However, this comes with the additional probe manipulation within the rectum and additional biopsies of suspicious areas, which has been associated with greater patient pain and anxiety (Chesnut, 2020).

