### **Periprocedural Intervention**

The patient will be moved to the biopsy room and standard procedure for lateral positioning and explaining prostate biopsy will be done in the routine manner preferred by the individual Urologist. Oxygen saturation monitor will be applied to the patient's finger and monitored throughout the procedure. The patient's heart rate will also be monitored accordingly.

The inhalation gas mask will be positioned on the patient's face, and the patient will then be instructed to begin breathing as previously instructed. Initially the patient will receive 100% oxygen at 10 Liters/minute. In the control group, this will be continued throughout the procedure.

After the Urologist describes the procedure, the SANO group will have nitrous oxide turned on to 30%, ensuring that the patient is relaxed but still conversant through the procedure. The nitrous will be adjust up or down based on the patient's response to the question "are you feeling the nitrous" and "are you happy at this level". The range will be between 25 - 45%. This may take 2-3 minutes. Both groups will be asked these questions. Both groups will be asked to take several deep breaths before inserting the rectal probe. The prostate biopsy for both study and control participants will include the normal routine administration of local peri-prostatic nerve block using preferred technique of the individual Urologist. During the procedure, the patient and patient's oxygen saturation will be monitored by a [name], APP, or MD (separate from MD performing the procedure) and if at any point in time the patient is unhappy with gas inhalation, the observer will aid the patient in removing the mask. At the end of the procedure, the SANO group will be turned down to 0% nitrous oxide, and 100% oxygen will be administered through the mask for an additional 2-3 minutes as the patient is cleaned up and repositioned to the supine position. Assessment of the "time in" and "time out" of the procedure room will be recorded.

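### The only stated duration analysis for Aim 2 compares gas patients with self-selected decliners, unadjusted; the randomised SANO-versus-oxygen time difference is not named, and nothing bars reading non-significance as no burden.

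*Combined protocol and SAP*

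**What the plan says.** Under Specific Aims, Aim 2 is "To demonstrate that the SANO at the time of prostate biopsy does not significantly increase burden on Urologist productivity", and its first hypothesis is "Administration of periprocedural SANO will not significantly lengthen the time of the procedure relative to local anesthetic alone".

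The Data Analysis section (B3.B) gives duration one sentence. It opens "Additional metric will include duration of biopsy", defines duration from entry to and exit from the procedure room, and takes patients given nitrous or control oxygen "when compared to patients who do not consent to the study (and will have no gas applied"). It states no adjustment, test, confidence interval or margin for duration. It does not say whether the two gas arms are pooled or taken separately. The same section does name a between-arm comparison for the VAS and VAS-A scores, and it compares the situational pain catastrophizing score for both groups.

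Periprocedural Intervention (B3.A) says that room entry and exit times are recorded. It also describes what the oxygen arm shares with SANO. Both start on oxygen through the mask, and for oxygen patients "In the control group, this will be continued throughout the procedure". On the titration questions, "Both groups will be asked these questions".

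**The concern.** Aim 2 supports the claim that SANO can be adopted without slowing a clinic. Three features of the plan weaken that claim.

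- **Self-selection.** Patients who decline may differ from those who join. Subject Population admits both sextant and MRI-fusion biopsies, and the Background says that fusion brings "additional probe manipulation within the rectum and additional biopsies of suspicious areas". Positioning and explanation in the biopsy room "will be done in the routine manner preferred by the individual Urologist". If biopsy type or urologist differs between joiners and decliners, room time may differ for reasons unrelated to gas.
- **The randomised contrast is not named.** The trial has a comparison of room time that is free of self-selection, and its data are already collected, but the plan does not commit to reporting it.
- **No rule for the conclusion.** The aim is to demonstrate the absence of a significant increase. Without a stated rule, a non-significant test could be offered as that demonstration, however imprecise the estimate.

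**Working it through.** **1. The plan's own figure.** Sample Size Justification uses a 4-point difference, SD 8, alpha 0.05 and 80% power. A two-sided two-sample t-test needs 63.8, so 64 per group. Allowing for 15% loss, 64 / 0.85 = 75.3, so 76 per group and 152 in all. Both figures reproduce. They are sized for half an SD on a score; no sample size is given for time.

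**2. Assumed inputs for time.** The documents give no mean or SD for room time, so SDs of 10, 7 and 5 minutes are shown, always in that order. Periprocedural Intervention allows 2-3 minutes for adjusting the nitrous level and 2-3 minutes on oxygen at the end, the latter overlapping clean-up. True delays of 2 and 4 minutes are therefore used as illustrations.

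**3. How often a real delay is non-significant.** Chance = 1 − power of a two-sample t-test (two-sided 0.05, noncentral t, effect size = delay / SD), 76 per arm.

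| True delay | SD 10 | SD 7 | SD 5 |
|---|---|---|---|
| 2 min | 77% | 58% | 31% |
| 4 min | 31% | 6% | 0.2% |

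So non-significance says little about a short delay unless times vary little.

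**4. What an interval would show.** 95% half-width = t(0.975) × SD × √(2/n). With n = 76 and SD 10: 1.976 × 10 × √(2/76) = 1.976 × 10 × 0.1622 = 3.2 minutes. For SDs of 7 and 5 it is 2.2 and 1.6 minutes. With 64 evaluable per arm the three values are 3.5, 2.45 and 1.75 minutes. The interval tells the reader directly which delays remain possible.

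**5. Self-selection, in both directions.** Expected unadjusted difference = true delay − (decliners' extra minutes from case mix). A larger sample does not remove the second term. Take a 2-minute case-mix difference as an illustration.
- Decliners run 2 minutes longer and SANO truly adds 2: expected difference 2 − 2 = 0. The delay disappears.
- Decliners run 2 minutes shorter and SANO adds nothing: expected difference 0 + 2 = 2. With 76 in each group, the table above gives a significant false delay in 100 − 77 = 23%, 100 − 58 = 42% and 100 − 31 = 69% of trials.

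The number of decliners and the size and sign of any case-mix difference are not in the documents.

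**6. Pooling.** If SANO adds d minutes and oxygen adds none, pooling the arms at 1:1 gives an expected difference of (d + 0) / 2 = d/2. A 2-minute nitrous delay would appear as 1 minute.

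**7. What each contrast estimates.** SANO versus oxygen isolates nitrous, because the mask and the questions are common to both arms. SANO versus no gas includes the mask set-up but is not randomised. Neither replaces the other.

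**The case against.** The strongest reply is that the comparator follows from the hypothesis. The hypothesis concerns local anaesthetic alone, and oxygen patients also wear the mask and answer the same questions, so the randomised contrast removes set-up time that a clinic would bear. That stands: a reader might infer that using a no-gas group is itself the error, and the documents do not support this.

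It is also fair to say that the Data Analysis sentence mentions both arms beside the no-gas group, so a three-group comparison is a natural reading. A reader might infer that the randomised difference will go unreported or that pooling is planned. The text establishes only that the difference is not named and that pooling is left open.

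The self-selection evidence is limited. The Background links fusion to more pain and anxiety, and longer duration is an inference from the extra manipulation and cores. Nothing shows that consent varies with biopsy type, and bias could favour or penalise SANO. This limits the point to an unaddressed risk.

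Finally, the plan names no test for any outcome, and duration is an additional metric, so a formal margin could be called reviewer preference. That largely stands. A margin on the randomised difference would also tie a claim about local anaesthetic alone to a contrast that does not estimate it. What remains is the aim's wording about demonstrating no burden, which restraint in interpretation and a confidence interval can address.

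**Conclusion.** The point holds as a minor one. As written, a conclusion that SANO adds no time could rest on case mix or on an imprecise non-significant result, while a randomised estimate from recorded data is not committed to. The 2-minute figures (77%, 58% and 31% non-significant) depend on the assumed SDs and delay and are illustrative. The structural gap does not depend on them.

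Two stronger readings are not supported. One is that the trial's main result is compromised: the anxiety and pain comparison is randomised and does not use the decliners. The other is that decliners' data would be gathered without provision. The Consent section describes consent for participants, and no section that can be read describes collecting times on those who decline. But the consent pages and the study flowchart are not available here, so this is a query to the sponsor and not a finding.

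**What to change.** 1. Add to Data Analysis: the SANO-versus-oxygen difference in room time will be reported with its 95% confidence interval, with a note that it isolates nitrous and not the mask set-up shared by both arms.
2. Keep the no-gas comparison, with SANO shown separately from oxygen, adjusted for biopsy type (sextant or MRI-fusion) and urologist, and labelled non-randomised and supportive.
3. State that a non-significant difference will not be read as no added burden, and that conclusions will rest on the estimates and their intervals.
4. Ask the sponsor whether room time, biopsy type and urologist may be collected for patients who decline, and under what provision.

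Items 1 and 3 are analysis-plan wording only, since times in both arms are already recorded. Item 2 may need protocol text, depending on the answer to item 4. The one cost is that a no-burden claim becomes harder to assert.
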